7.1 Nivolumab and Ipilimumab Dose Modifications

Below are dose modification tables for nivolumab and combination nivolumab with ipilimumab for the following adverse events. Please use as written and contact the drug monitor for any proposed changes.

Please refer to Appendix B, the Nivolumab Investigator's Brochure, or the Ipilimumab Investigator's Brochure for toxicity management algorithms which include specific treatment guidelines. These algorithms should be followed unless there are specific clinical circumstances for which the treating physician decides an alternative treatment approach is clinically appropriate. Consultation with the study PI or drug monitor is recommended.

In several places there are differences from the algorithms regarding protocol directed drug modifications and these are identified with (#). In these cases, please follow the protocol-specific guidelines in this section.

Generally, early evaluation while withholding drug, and appropriate treatment as indicated in the management tables and event specific guidelines is strongly encouraged.

- Any patient with grade 2 drug-related uveitis, eye pain, or blurred vision that does not respond to topical therapy and does not improve to grade 1 severity within the re-treatment period OR that requires systemic treatment should go off protocol therapy
- Patients with any AE, laboratory abnormality, or intercurrent illness which, in the judgment of the investigator, presents a substantial clinical risk to the patient with continued study drug dosing should go off protocol therapy.
- Any grade 3 or 4 drug-related laboratory abnormality or electrolyte abnormality that can be managed independently from underlying organ pathology with electrolyte replacement, hormone replacement, or insulin therapy, or that does not require treatment **does not** require discontinuation of protocol therapy.
- If any kidney-related AEs (e.g. elevated serum creatine levels, development of DSA or non-HLA antibodies, or development of severe proteinuria [>1 g/day]) are observed, nivolumab should be held, a renal allograft biopsy should be obtained, and treatment for allograft rejection should be started immediately (see Section 7.2).

Skin Rash and Oral Lesions	Management/Next Dose for Nivolumab and Combination Nivolumab/Ipilimumab
≤ Grade 1	No change in dose*
Grade 2	Hold* until ≤ grade 1 (#). Resume at same dose level.
Grade 3	Hold* until ≤ grade 1. Resume at same level at investigator's discretion

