Grade 4	Off protocol therapy
*Patients with purpuric or bullous lesions must be evaluated for vasculitis, Steven-Johnson syndrome, TEN, and autoimmune bullous disease including oral lesions of bullous pemphigus/pemphagoid. Pruritus may occur with or without skin rash and should be treated symptomatically if there is no associated liver or GI toxicity. Note skin rash typically occurs early and may be followed by additional events particularly during steroids tapering.	
Recommended management: See Skin AE management guidelines.	

Liver Function AST, ALT, Bilirubin	Management/Next Dose for Nivolumab and Combination Nivolumab/Ipilimumab
≤ Grade 1	Hold, at investigator's discretion, until values return to ULN or baseline (#). Resume at same dose level.
Grade 2 (3 – 5 × ULN)	Hold until values return to baseline. Resume at same dose level.
Grade 3 (5 – 20 × ULN)	Hold until grade 1 (ULN – 3 x ULN) or baseline. Resume at same dose level, at investigator's discretion. If persistent (>7 days) or requires steroids, patients should go off protocol therapy
Grade 4	Off protocol therapy
Continued treatment of active immune mediated hepatitis may exacerbate ongoing inflammation. Holding drug to evaluate LFT changes and early treatment are recommended. LFT changes may occur during steroid tapers from other events and may occur together with other GI events including cholecystitis/pancreatitis.	
Note: Grades for liver function follow multiples of ULN, rather than multiples of baseline.	
Recommended management: See Hepatic AE Management Algorithm.	

Diarrhea/Colitis	Management/Next Dose for Nivolumab and Combination Nivolumab/Ipilimumab
≤ Grade 1	Hold until baseline (#). No change in dose.
Grade 2	Hold until baseline. No change in dose.
Grade 3	Resume at same dose level, at investigator discretion, if resolved within 7 days without steroids and with no evidence of colitis. If persistent (>7 days), or requires steroids, patients should go off protocol therapy.
Grade 4	Off protocol therapy

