Patients on IV steroids may be switched to an equivalent dose of oral corticosteroids (e.g. prednisone) at start of tapering or earlier, once sustained clinical improvement is observed. Lower bioavailability of oral corticosteroids should be taken into account when switching to the equivalent dose of oral corticosteroids.

Hepatic Adverse Event Management Algorithm

Rule out non-inflammatory causes. If non-inflammatory cause, treat accordingly and continue I-O therapy. Consider imaging for obstruction.

[figure not shown]
Patients on IV steroids may be switched to an equivalent dose of oral corticosteroids (e.g. prednisone) at start of tapering or earlier, once sustained clinical improvement is observed. Lower bioavailability of oral corticosteroids should be taken into account when switching to the equivalent dose of oral corticosteroids.

*I-O therapy may be delayed rather than discontinued if AST/ALT \leq 8 x ULN and T.bili \leq 5 x ULN.

**The recommended starting dose for grade 4 hepatitis is 2 mg/kg/day methylprednisolone IV.

Neurological Adverse Event Management Algorithm

[figure not shown]
Rule out non-inflammatory causes. If non-inflammatory cause, treat accordingly and continue I-O therapy.

Patients on IV steroids may be switched to an equivalent dose of oral corticosteroids (e.g. prednisone) at start of tapering or earlier, once sustained clinical improvement is observed. Lower bioavailability of oral corticosteroids should be taken into account when switching to the equivalent dose of oral corticosteroids.

Pulmonary Adverse Event Management Algorithm

[figure not shown]
Rule out non-inflammatory causes. If non-inflammatory cause, treat accordingly and continue I-O therapy. Evaluate with imaging and pulmonary consultation.

Patients on IV steroids may be switched to an equivalent dose of oral corticosteroids (e.g. prednisone) at start of tapering or earlier, once sustained clinical improvement is observed. Lower bioavailability of oral corticosteroids should be taken into account when switching to the equivalent dose of oral corticosteroids.

Renal Adverse Event Management Algorithm

[figure not shown]
Rule out non-inflammatory causes. If non-inflammatory cause, treat accordingly and continue I-O therapy

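### The Grade 3 liver row in Section 7.1 and the Appendix B hepatic footnote set different limits for re-dosing, and no stated rule says which governs

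*Combined protocol and SAP*

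**What the plan says.** The liver table in Section 7.1 is headed AST, ALT and bilirubin and covers both nivolumab alone and the combination. Its Grade 3 row, printed as 5–20 × ULN, says: "Hold until grade 1 (ULN – 3 x ULN) or baseline". After that the investigator may choose to restart without a dose change. The row then sets the exit: "If persistent (>7 days) or requires steroids, patients should go off protocol therapy". The table ends by sending the reader to the hepatic algorithm for management.

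That algorithm, in Appendix B, carries an asterisked footnote: "I-O therapy may be delayed rather than discontinued if AST/ALT" is at most 8 × ULN and total bilirubin is at most 5 × ULN.

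The text before the tables in Section 7.1 describes how the two sources relate: "In several places there are differences from the algorithms regarding protocol directed drug modifications and these are identified with" (#). It continues: "In these cases, please follow the protocol-specific guidelines in this section". The same text asks sites to apply the tables unchanged and take any proposed change to the drug monitor. It also asks them to follow the algorithms unless particular clinical circumstances justify something else. Section 6.7 (Duration of Therapy), in its list of reasons to end treatment, refers to both Section 7 and the Appendix B algorithms for adverse events that require permanent discontinuation.

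**The concern.** A site that opens the table finds a discretionary hold-and-resume rule for the whole of 5–20 × ULN. A site that follows the table's own pointer to the hepatic algorithm finds that delay is available only up to 8 × ULN for AST/ALT and 5 × ULN for bilirubin. The protocol says such differences will be flagged, and this one is not. A reader cannot tell whether it is intended.

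What is at stake is re-dosing after a hepatic immune toxicity. The liver table itself warns that continuing drug during active immune-mediated hepatitis may make it worse. The current amendment adds immune-mediated hepatitis to the nivolumab risk list (Section 10.1.1), and hepatitis is already listed for ipilimumab (Section 10.1.2). Two sites could handle the same event in opposite ways, and each could point to protocol text in support.

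**Working it through.** The plan gives no figure to reproduce. The check sets the two rules side by side and then looks for a rule of precedence.

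| | Section 7.1, Grade 3 liver row | Appendix B, hepatic footnote |
|---|---|---|
| AST/ALT | 5–20 × ULN: hold, may resume | delay possible up to 8 × ULN |
| Bilirubin | 5–20 × ULN (same printed band) | delay possible up to 5 × ULN |
| Other conditions | not beyond 7 days, no steroids, investigator's discretion | both laboratory limits must be met |
| Otherwise | off protocol therapy | discontinuation, by implication |

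**Step 1, AST/ALT.** The table's range is 5 to 20 × ULN and the footnote's is up to 8 × ULN. Both allow delay from 5 to 8 × ULN, provided bilirubin is at most 5 × ULN. They differ above 8 and up to 20 × ULN. Exactly 8 × ULN is not in conflict.

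**Step 2, bilirubin.** On the row's printed band the table's range is 5 to 20 × ULN and the footnote's is up to 5 × ULN. They meet only at 5 × ULN itself, so every bilirubin value above 5 × ULN in that band is in conflict. The row does not say whether one band is meant to serve both AST/ALT and bilirubin.

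**Step 3, the table's own exits.** If the event lasts more than 7 days or needs steroids, the table also takes the patient off protocol therapy. Above the footnote's limits the two texts then agree. The conflict operates only for events that settle within 7 days without steroids.

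**Step 4, the (#) mark.** It appears on skin Grade 2, on liver Grade 1 or lower, and on diarrhea Grade 1 or lower. Within the liver table the mark is therefore in use, but not on the Grade 3 row.

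**Step 5, precedence.** Four provisions bear on the question:

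- The (#) rule gives precedence to Section 7.1 only where the mark is present.
- The instruction to apply the tables unchanged favours the table.
- The instruction to follow the algorithms favours Appendix B.
- The note that opens Section 7, on conflicting recommendations, covers a patient with several adverse events. It does not cover one event with two rules.

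None of these settles an unmarked difference.

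**The case against.** The strongest reply is that the two texts do different jobs: the Section 7.1 tables decide the next dose, and Appendix B decides how to treat the toxicity. The table's column heading covers management and next dose, and it cites the algorithm only for recommended management. A site could reasonably read it that way. The protocol does not keep to that division, however. Section 6.7 names both sources for permanent discontinuation, and Section 6.3 sends toxicity management for the combination to both. The footnote itself is about delaying or discontinuing drug.

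Several further points stand and narrow the concern:

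- Appendix B says therapy continues when the cause is non-inflammatory, so those events do not reach the footnote's limits.
- A separate bullet in Section 7.1 says that a drug-related Grade 3 or 4 laboratory abnormality needing no treatment does not require discontinuation. It points the same way as the table, but it does not mention the algorithm and so leaves the relation to Appendix B open.
- Section 7.1 recommends consulting the study PI or drug monitor, which may bring sites into line. It is a recommendation, not a requirement.
- The hepatic flowchart is not shown in the text available here. The box that the asterisk belongs to cannot be seen, and that box may carry its own conditions.

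A reader might also infer that Section 7.1 defers to Appendix B wherever the (#) is absent, so that the footnote simply governs. The instruction to apply the tables unchanged, and the exception for clinical circumstances, do not support that. The accurate statement is that precedence is not given.

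**Conclusion.** The point holds as an unmarked internal conflict about re-dosing. It covers AST/ALT above 8 and up to 20 × ULN, or bilirubin above 5 × ULN on the printed band, in events that settle within 7 days without steroids. It applies to monotherapy and to the combination.

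It rests on one inference: that allowing delay instead of discontinuation up to the limits means discontinuation above them. The visible hepatic text does not say so outright, and the sponsor should check it against the flowchart.

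Two larger claims are tempting and are not supported:

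- The AST/ALT conflict spans (20 − 8) / (20 − 5) = 12/15 = 80% of the Grade 3 band. That is the width of an interval, not a share of patients or events. The documents give no rate of Grade 3 hepatic events, so the frequency is unknown.
- A reader might infer that the conflict could shift the decision made at 5 successes among 16 patients. No route to that is shown. Section 6.2 places the week-16 assessment regardless of the number of doses received. Section 9.4 makes a patient evaluable after one nivolumab dose with tumor and graft assessments at about 8 and 16 weeks. Stopping nivolumab for a liver event is in itself neither a failure nor an exclusion.

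The case for correction is therefore safety and consistent handling across sites. No view is taken on which rule is right.

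**What to change.** Reconcile the Grade 3 liver row in Section 7.1 with the hepatic footnote in Appendix B. Either state the same limits in both places or, if the difference is intended, mark the row (#) so that the existing precedence rule applies. In either case, make clear whether the limits for AST/ALT and for bilirubin differ. Check the footnote against its flowchart before editing. The clinical team decides which rule applies.

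The cost is one table row or one mark in an amendment. Sample size and data collection are unaffected.

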See GI AE Algorithm for management of symptomatic colitis. Patients with Grade 2 symptoms but normal colonoscopy and biopsies may be retreated after resolution. Patients who require systemic steroids should be taken off study treatment. If possible without compromising acute care, evaluate pituitary function prior to starting steroids. Evaluation for all patients for additional causes includes C. diff , acute and self-limited infectious and foodborne illness, ischemic bowel, diverticulitis, and IBD.	
Recommended management: See GI AE Management Algorithm.	

Pancreatitis Amylase/Lipase	Management/Next Dose for Nivolumab and Combination Nivolumab/Ipilimumab
≤ Grade 1	Continue at same dose level, if asymptomatic, at investigator's discretion.
Grade 2	Continue at same dose level, if asymptomatic, at investigator's discretion. If symptomatic, resume at same dose level once resolved.
Grade 3	Continue at same dose level, if asymptomatic, at investigator's discretion. Patients should have imaging done when clinically indicated (i.e. , grade 3 pancreatitis) before resuming treatment. Patients who develop symptomatic pancreatitis or diabetes mellitus should go off protocol therapy.
Grade 4	Hold until grade 2. Resume at same dose level if asymptomatic. Patients should have imaging done before resuming treatment, and when clinically indicated. Patients who develop symptomatic pancreatitis or diabetes mellitus should go off protocol therapy.
Patients may develop symptomatic and radiologic evidence of pancreatitis as well as DM and diabetic ketoacidosis (DKA). Lipase elevation may occur during the period of steroid withdrawal and with other immune mediated events or associated with colitis, hepatitis, and patients who have asymptomatic lipase elevation typically have self-limited course and may be re-treated. For treatment management of symptomatic pancreatitis please follow the Hepatic AE Management Algorithm.	

Pneumonitis	Management/Next Dose for Nivolumab and Combination Nivolumab/Ipilimumab
≤ Grade 1	Hold dose pending evaluation and resolution to baseline including baseline O2 saturation. Resume with no change in dose after pulmonary and/or infectious disease consultation excludes lymphocytic pneumonitis.

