Grade 2	Hold dose pending evaluation. Resume with no change in dose after pulmonary and/or infectious disease consultation excludes ipilimumab and associated lymphocytic pneumonitis as the cause of the pneumonitis. Patients should go off protocol therapy if steroids are required.
Grade 3	Hold dose pending evaluation. Resume with no change in dose after pulmonary and/or infectious disease consultation excludes ipilimumab and associated lymphocytic pneumonitis as the cause of the pneumonitis. Patients should go off protocol therapy if steroids are required.
Grade 4	Off protocol therapy.
Distinguishing inflammatory pneumonitis is often a diagnosis of exclusion for patients who do not respond to antibiotics and have no causal organism identified including influenza. Most patients with respiratory failure or hypoxia will be treated with steroids. Bronchoscopy may be required and analysis of lavage fluid for lymphocytic predominance may be helpful. Patients with new lung nodules should be evaluated for sarcoid-like granuloma. Seasonal influenza killed vaccine should be recommended for all patients.	
Recommended management: See Pulmonary AE Management Algorithm.	

Other GI / Nausea and Vomiting	Management/Next Dose for Nivolumab and Combination Nivolumab/Ipilimumab
≤ Grade 1	No change in dose.
Grade 2	Hold pending evaluation for gastritis, duodenitis, and other immune AEs or other causes. Resume at same dose level after resolution to ≤ grade 1.
Grade 3	Hold pending evaluation until ≤ grade 1. Resume at same dose level. If symptoms do not resolve within 7 days with symptomatic treatment, patients should go off protocol therapy.
Grade 4	Off protocol therapy.
Patients with Grade 2 or 3 nausea or vomiting should be evaluated for upper GI inflammation and other immune related events.	

Fatigue	Management/Next Dose for Nivolumab and Combination Nivolumab/Ipilimumab
≤ Grade 1	No change in dose.
Grade 2	No change in dose.
Grade 3	Hold until ≤ grade 2. Resume at same dose level.
Grade 4	Off protocol therapy.
Fatigue is the most common adverse event associated with immune checkpoint therapy. Grade 2 or greater fatigue should be evaluated for associated or underlying organ involvement including pituitary, thyroid, or hepatic; or muscle inflammation (as assessed by creatine phosphokinase levels).	

Neurologic Events	Management/Next Dose for Nivolumab and Combination Nivolumab/Ipilimumab

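### The Grade 2 and Grade 3 pneumonitis rows also govern nivolumab alone, yet ipilimumab is the only drug they name for exclusion before restart

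*Combined protocol and SAP*

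**What the plan says.** Section 7.1 introduces its tables as applying to nivolumab and to the combination, and the pneumonitis table's column header repeats both. Sites are told: "Please use as written and contact the drug monitor for any proposed changes".

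The table has four rows:

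- **Grade 1 or lower.** "Hold dose pending evaluation and resolution to baseline including baseline O2 saturation". Then: "Resume with no change in dose after pulmonary and/or infectious disease consultation excludes lymphocytic pneumonitis". No drug is named.
- **Grades 2 and 3 (identical text).** The dose is held pending evaluation. Then: "Resume with no change in dose after pulmonary and/or infectious disease consultation excludes ipilimumab and associated lymphocytic pneumonitis as the cause of the pneumonitis". Both rows add: "Patients should go off protocol therapy if steroids are required".
- **Grade 4.** Off protocol therapy.

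The note under the table describes inflammatory pneumonitis as often a diagnosis of exclusion and mentions lavage for lymphocytic predominance. It adds: "Most patients with respiratory failure or hypoxia will be treated with steroids". It then refers sites to the Pulmonary algorithm in Appendix B.

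**The concern.** The rule for the more severe grades names a drug that most patients governed by it will not have received. A consultant who can say only that ipilimumab is not responsible has met the named-drug part of the condition. The rows do not expressly ask about the drug the patient is taking.

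The stake is re-exposure to nivolumab after a Grade 2 or 3 lung event that nivolumab may have caused. In Section 10.1.1 pneumonitis carries the footnote warning of severe and possibly fatal immune-mediated events. Sites could also differ, some reading nivolumab into the row and others following its literal text.

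**Working it through.** There is no planned figure to reproduce. The check is a comparison of texts, followed by one bounding calculation.

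**1. Do the rows govern monotherapy?** Yes. The header and the opening of Section 7.1 both say so. Section 6.3 also says that toxicity under the combination is managed by the same guidance as for nivolumab alone.

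**2. Will monotherapy patients have had ipilimumab?** Normally not. Section 6.1 starts everyone on nivolumab with tacrolimus and prednisone. Section 6.3 offers ipilimumab only after progression or allograft loss. Section 3.2.6 bars earlier anti-CTLA-4 treatment, but only for the current cancer, so use for a previous cancer is not strictly ruled out.

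**3. What must be excluded before restart?**

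| Row | Drug named | Other cause named |
|---|---|---|
| Grade 1 or lower | none | lymphocytic pneumonitis |
| Grade 2 | ipilimumab only | 'associated' lymphocytic pneumonitis |
| Grade 3 | ipilimumab only | 'associated' lymphocytic pneumonitis |

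Three rows permit restart, and 2 of the 3 name only ipilimumab. With no ipilimumab exposure, that part is satisfied without any clinical finding. The word 'associated' follows ipilimumab, so the second part need not be read as covering nivolumab.

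**4. Is nivolumab a recognised cause?** Yes. Its list in Section 10.1.1 has pneumonitis in the column headed Less Likely (<=20%), with the immune-mediated footnote.

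**5. Which other rules catch the patient?**

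- The steroid stop removes anyone who needs steroids, and the table note expects that of most hypoxic patients.
- An investigator must withdraw a patient with any event that "presents a substantial clinical risk to the patient with continued study drug dosing should go off protocol therapy".
- Section 6.5 requires non-drug-related pulmonary toxicity to return to baseline before restart. Its separate grade 1 or baseline rule is for events that are not autoimmune or inflammatory. A pneumonitis that is inflammatory and due to nivolumab falls under neither.

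This leaves a Grade 2 or 3 event, managed without steroids, with nivolumab not ruled out.

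**6. How many patients?** All 16 planned patients are under these rows before any on-study ipilimumab. At the column limit, the expected number with pneumonitis of any grade is 16 x 0.20 = 3.2. That is the edge of a category in general nivolumab experience. It is not an observed rate, nor one for transplant recipients. The share that is Grade 2 or 3 and managed without steroids is not given, so no estimate of the affected number is possible.

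**The case against.** The best defence is that no pulmonologist would treat exclusion of a drug never given as clearance. The row also asks about lymphocytic pneumonitis, the note frames the work-up without naming a drug, and the Grade 1 row is drug-neutral. Consultation with the study PI or drug monitor is recommended, and the residual case needs several conditions to coincide. Much of this stands. It makes a wrong restart unlikely and keeps the point small. It does not correct rows that sites are told to apply as they stand.

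A reader might also infer a second defect: that Grades 2 and 3 have no recovery level, so a sicker patient could restart under a looser standard than a Grade 1 patient. The documents do not support that, for two reasons. First, once a drug cause has been excluded, the event is non-drug-related and Section 6.5 already requires return to baseline. Second, on the algorithms Section 7.1 says: "In several places there are differences from the algorithms regarding protocol directed drug modifications and these are identified with" the mark (#). The pneumonitis rows carry no such mark, so a recovery level in the Pulmonary algorithm would apply. Its figure is not shown in the available text, so absence of a level cannot be established.

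**Conclusion.** The concern holds for the drug named. In the Grade 2 and Grade 3 rows the exclusion test names only ipilimumab, and for a patient on the main regimen with no ipilimumab exposure that test is met automatically. The missing recovery level in those two cells is not a separate defect.

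This rests on a literal reading of the rows, which Section 7.1 invites, and on the patient not having had ipilimumab for an earlier cancer. A recovery level in the unseen Pulmonary figure would not by itself correct the drug named in the rows.

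The size is minor: two table cells and a residual group of unknown, probably small, number. It would be wrong to infer that the protocol intends rechallenge after nivolumab pneumonitis, or that 3.2 patients are affected. The primary endpoint, type I error and power are untouched.

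**What to change.** In both the Grade 2 and the Grade 3 rows, replace what the consultation must exclude with: *nivolumab and/or ipilimumab, and lymphocytic pneumonitis*. Leave the rest of the restart sentence and the steroid stop unchanged.

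The drugs and lymphocytic pneumonitis should stay as two separate items. Wording that excluded only drug-associated lymphocytic pneumonitis would let non-lymphocytic drug injury through, and bronchiolitis obliterans with organizing pneumonia is on both drugs' risk lists.

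As an optional consistency edit, the Grade 1 recovery condition (baseline, including oxygen saturation) could be repeated in the two rows. Check it first against the Pulmonary algorithm. If the algorithm sets a different level, use that level or mark the rows (#).

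The cost is two cells in the next amendment and no new procedures. A patient whose Grade 2 or 3 pneumonitis is attributed to nivolumab would not restart, even if it settled without steroids. The rows already set that bar for ipilimumab.
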